5. LIST OF ABBREVIATIONS

AE/AER/EAE	Adverse Event / Adverse Event Report / Expedited Adverse Event
AFB	Acid Fast Bacilli
AIDS	Acquired Immunodeficiency Syndrome
ALT/SGPT	Alanine Aminotransferase
ART/ARV	Antiretroviral Therapy / Antiretroviral
AST/SGOT	Aspartate Aminotransferase
AUC	Area Under the time-concentration Curve
CBC	Complete Blood Count
CDC	(US) Centers for Disease Control and Prevention
Cmax	Maximum concentration
CRF	Case Report Form
CXR	Chest X-ray
DBS	Dried Blood Spot
DOT	Directly Observed Therapy
DR-TB	Drug-Resistant Tuberculosis
DS-TB	Drug-Susceptible Tuberculosis/Drug-Sensitive Tuberculosis
DSMB	Data and Safety Monitoring Board
DST	Drug Susceptibility Testing
EC	Ethics Committee
E/CIA	Chemiluminescence immunoassay
FDA	(US) Food and Drug Administration
H/INH	Isoniazid
HBSAG	Hepatitis B Surface Antigen
HHC	Household contact
HIV	Human Immunodeficiency Virus
HP	Isoniazid and Rifapentine
IoR	Investigator of Record
IPT	Isoniazid Preventive Therapy
IRB	Institutional Review Board
LFT(s)	Liver Function Test(s)
LTBI	Latent Tuberculosis Infection
MDR-TB	Multidrug-Resistant Tuberculosis
MIC	Minimum Inhibitory Concentration
MOP	Manual of Operations
M.tb.	Mycobacterium tuberculosis
P/RPT	Rifapentine
PI	Principal Investigator
РК	Pharmacokinetics
RIF	Rifampin/Rifampicin
SAE	Serious Adverse Event
SOC	Standard Of Care
SOE	Schedule of Evaluations
SOP	Standard Operating Procedure

T1/2	Half-life
TB	Tuberculosis
TBTC	Tuberculosis Trials Consortium
TPT	TB Preventive Therapy
ULN	Upper Limit of Normal
WHO	World Health Organization
XDR-TB	Extensively Drug Resistant Tuberculosis

6. PROTOCOL SUMMARY

Protocol Title:	Treatment Success and Safety of 4 Weeks of Daily Rifapentine and Isoniazid (1HP) vs. 12 weeks of Weekly Rifapentine and Isoniazid (3HP) for Prevention of Tuberculosis in HIV-uninfected Individuals (1v3HP for TPT in HIV-uninfected individuals): Ultra Curto
Treatment Indication:	TB preventive treatment (TPT) in HIV uninfected persons age ≥15 years with LTBI
Trial Objective:	To compare treatment success (adherence and completion of treatment) and safety of 1HP with 3HP in HIV-uninfected adults and adolescents at increased risk of TB.
Trial Design:	An international, multicenter, randomized, controlled, open-label, two arm, Phase IV clinical trial. Arm A (n=250) : Experimental arm. Rifapentine 600 mg daily and isoniazid 300 mg daily for 4 weeks
	Arm B (n=250) : Control arm. Rifapentine 900 mg and isoniazid 900 mg weekly for 12 weeks.
Sample Size	500
Patient Population:	The study will enroll HIV-uninfected individuals who are ≥ 15 years old, and are candidates to receive TB preventive therapy (i.e. LTBI with no evidence of active TB). Key exclusion criteria include HIV infection, abnormal liver enzymes, neutropenia, previous treatment of TB or latent TB infection, or a history of study drug intolerance.
Study treatment:	TB preventive treatment: Arm A (n=250) : Experimental arm. Rifapentine 600 mg daily and isoniazid 300 mg daily for 4 weeks. Arm B (n=250) : Control arm. Rifapentine 900 mg weekly and isoniazid 900 mg weekly for 12 weeks.
Trial sites:	 Health units from Rio de Janeiro Health Secretariat and NARDOT study slinis, Rio de Janeiro, Brazil

Criteria for evaluation:

Primary Objectives:

To compare treatment success (completion of treatment with \geq 90% adherence) of 1HP compared with 3HP in HIV-uninfected adults and adolescents at increased risk of TB.

To compare the safety of 1HP vs 3HP in HIV-uninfected adults and adolescents at increased risk of TB.

Primary Outcomes:

(1) Successful completion of TPT with \geq 90% adherence documented by self-report, pill count, and pharmacologic monitoring.

(2) Safety of treatment regimens, defined as occurrence of Grade 2 or higher targeted safety events while taking study medications or within 14 days of stopping, or discontinuation of study medications because of side effects.

Targeted safety events are hypersensitivity syndrome, rash, peripheral neuropathy, hepatotoxicity, nausea and vomiting, and drug-related fever.

Secondary Outcome:

- (1) Incremental cost-effectiveness of 1HP and 3HP (compared to each other, 6H, and no treatment) using a societal perspective.
- (2) Analyze, in each of the health units in the study, the time needed to provide comprehensive care to patients.

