8.3 Secondary Outcome and Hypothesis

- (1) To compare the cost-effectiveness of 1HP and 3HP using a societal approach, modeling the incremental cost-effectiveness of 1HP vs 3HP, 6H, and no treatment.
- (2) Analyze, in each of the health units in the study, the time needed to provide comprehensive care to patients.

Hypothesis: We hypothesize that 1HP will be cost saving vs 3HP, v modelled costs of 6H and v no TPT.

A separate protocol will be prepared for this component of the study.

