10.3.2 Cost-Effectiveness

The primary outcome for the cost-effectiveness analysis will be the incremental costeffective ratio (ICER) per disability-adjusted life-year (DALY) averted by 1HP versus 3HP. The incremental cost-effectiveness ratio is defined as (total cost 1HP – total cost 3HP) / (total DALYs averted 1HP – total DALYs averted 3HP). Similar ICER estimates will be calculated to compare incremental DALYs averted by 1HP and 3HP versus 6H and no treatment. Additionally, the cost per treatment completed and cost per adverse event averted will be calculated for 1HP and 3HP, alongside estimates of the ICER values for each of these secondary cost-effectiveness outcomes comparing all treatment strategies.

Cost-effectiveness will be estimated using a Markov model to simulate a population of individuals eligible for TPT under each treatment strategy. Cost and effectiveness parameters (e.g. treatment costs, adherence, treatment completion) for the model will be taken from empiric values observed at each health unit participating in the Curto study. One-way and multi-way sensitivity analysis will be used to evaluate cost-effectiveness on specific model parameters, including but not limited to: discount rate, currency conversion rate, cadre of staff providing services, price of rifapentine, 1HP and 3HP completion rates, and 1HP and 3HP efficacy. A probabilistic sensitivity analysis using Monte Carlo simulation will be used to simulate the Markov model across ranges of all input parameters and build estimates of uncertainty around each cost and cost-effectiveness outcome. For each iteration, the Monte Carlo simulation will sample with replacement from a beta distribution for all model parameters empirically observed across Curto health units, with the mode at the median value observed. Uncertainty will be presented as 95% uncertainty intervals, defined as the observed value at the 2.5th and 97.5th percentiles for each outcome across the Monte Carlo iterations.

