Using the results of the Monte Carlo simulation, we will construct incremental costeffectiveness ratio planes and cost-effectiveness acceptability curves (CEACs) to demonstrate the probability of each strategy being cost-effective at different willingnessto-pay (WTP) thresholds. While we will consider a range of WTP thresholds in the primary analysis, we will use as our primary WTP threshold the most recent objective data on Brazil's country-specific WTP threshold. We will further report the probability of being cost-effective at WTP thresholds in \$500 increments (\$500, \$1000, etc). The ICER per DALY averted comparing 1HP to 3HP will be used for the primary ICER plane and CEAC.

Costs will be evaluated from the societal perspective, incorporating both costs to patients and to the healthcare system. Research costs will be excluded. Estimates of DALYs will be derived by combining literature values (TPT long-term effectiveness (Sterling, 2011), disability weights (Salomon, 2015)) with trial-based observations. We will use an analytic horizon of 5 years for tuberculosis events, with a lifetime horizon for TB-related sequelae, including death. The primary analysis will annuitize costs linearly using a 3% annual discount rate based on estimated life-years. In the analysis, costs will be presented in the latest year in which costs are measured during the trial, with costs collected in earlier years inflated using the World Bank's gross domestic product deflator for Brazil (https://data.worldbank.org/indicator/NY.GDP.DEFL.KD.ZG?locations=BR). All costs will then be converted to United States Dollars using the median World Bank conversion rate for that year (https://data.worldbank.org/indicator/PA.NUS.FCRF?locations=BR).

Time needed for care

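### SAP 10.3.2 compares four strategies pair by pair, with no dominance step and a primary acceptability curve for 1HP v 3HP only

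*Protocol*

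**What the plan says.** The Protocol Summary lists the outcome as "Incremental cost-effectiveness of 1HP and 3HP (compared to each other, 6H, and no treatment) using a societal perspective". Protocol 8.3 adds the expectation: "We hypothesize that 1HP will be cost saving vs 3HP, v modelled costs of 6H and v no TPT". Neither place sets a method; SAP 10.3.2 does:

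- The primary measure is the incremental cost-effectiveness ratio (ICER) per DALY averted for 1HP v 3HP: difference in total cost over difference in total DALYs averted.
- For the other two strategies, "Similar ICER estimates will be calculated to compare incremental DALYs averted by 1HP and 3HP versus 6H and no treatment". Together these cover five of the six possible pairs; 6H v no treatment is not listed.
- For cost per completed treatment and cost per adverse event averted, it plans "ICER values for each of these secondary cost-effectiveness outcomes comparing all treatment strategies", without saying how.
- Costs and effects come from a "Markov model to simulate a population of individuals eligible for TPT under each treatment strategy", with Monte Carlo sampling of the parameters.
- The curves are to "demonstrate the probability of each strategy being cost-effective at different" willingness-to-pay thresholds, but "The ICER per DALY averted comparing 1HP to 3HP will be used for the primary ICER plane and CEAC".

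Neither document mentions ordering the strategies, dominance, extended dominance, an efficiency frontier, or net benefit compared across all four.

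**The concern.** The four strategies are mutually exclusive. A ratio then guides a decision only when the comparator is the next best strategy still in contention. A strategy that costs more and averts less than another (dominated), or that is beaten by a mix of two others (extendedly dominated), should leave the list before ratios are formed. Ratios against a fixed comparator skip that step, so a strategy nobody should choose can still fall below the threshold.

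The plan's own expectations bring this close. If 1HP is cost saving against all three alternatives (Protocol 8.3, SAP 3.3) and its better completion (90% v 80%, SAP 3.2) carries through to DALYs, then 1HP dominates 3HP. The planned ratios of 3HP against 6H and against no treatment would then describe a strategy already ruled out. The primary ratio would be negative, a sign it would share with the opposite finding that 1HP costs more and averts less.

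The CEAC raises a related problem. In a curve built from 1HP v 3HP, neither 6H nor no treatment can win, whatever the threshold. The SAP also promises a probability for each strategy, but does not say against which set.

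**Working it through.** The documents state no ICER, cost or DALY by strategy, no probability, and no value for the primary threshold. There is no figure to reproduce. What follows is one logical result and three illustrations. **All inputs to the illustrations are assumptions, not trial figures.**

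**1. Bound.** Let net benefit NB = threshold × DALYs averted − cost. Whenever 1HP has the highest NB of the four, it also has a higher NB than 3HP. Hence P(1HP best of four) ≤ P(1HP beats 3HP). The two are equal when 6H and no treatment never win in draws where 1HP beats 3HP.

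**2. A dominated strategy with an acceptable ratio.** Assumed incremental cost and DALYs averted per 1,000 people:

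| Strategy | Cost | DALYs averted | NB at $1,000 |
|---|---|---|---|
| None | $0 | 0 | $0 |
| 6H | $30,000 | 60 | $30,000 |
| 3HP | $60,000 | 70 | $10,000 |
| 1HP | $55,000 | 80 | $25,000 |

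- 3HP costs more and averts less than 1HP, so it is dominated. Yet 3HP v none = 60,000/70 = $857, which passes a $1,000 threshold.
- 1HP v none = 55,000/80 = $688 also passes. But 6H v none = 30,000/60 = $500 and 1HP v 6H = 25,000/20 = $1,250, so at $1,000 the best choice is 6H.
- 1HP v 3HP = −5,000/10 = −$500. The reverse result, +5,000/−10, gives the same −$500.

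**3. Extended dominance.** Assume, per 1,000 people, a TB risk of 5%, and $1,000 and 2 DALYs per case. Cost per person, completion and efficacy are $60, 60%, 65% (6H); $110, 80%, 80% (3HP); $100, 90%, 80% (1HP). Total cost and DALYs averted are then none $50,000/0; 6H $90,500/39; 3HP $128,000/64; 1HP $114,000/72.

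- 6H v none = 40,500/39 = $1,038; 1HP v 6H = 23,500/33 = $712. The ratio falls as effect rises, so 6H is extendedly dominated.
- 3HP is dominated by 1HP. The only ratio left on the frontier is 1HP v none = 64,000/72 = $889.
- At $800, the 1HP v 6H ratio looks favourable, while the frontier selects no treatment.

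**4. Size of the CEAC gap.** 200,000 draws, with independent normal costs and DALYs.

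- A: means as in step 2; SD of cost $5,000 (6H) and $8,000 (3HP, 1HP); SD of DALYs 10; no treatment fixed at zero.
- B: 1HP cheapest and most effective. Mean costs for none, 6H, 3HP, 1HP are $80,000, $60,000, $60,000, $45,000, with SDs $10,000, $8,000, $8,000, $8,000. DALYs averted are 0, 50, 70, 80, with SD 10 (none fixed).
- C: as A, but 6H averts 30 DALYs.

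Each cell gives P(1HP beats 3HP) / P(1HP best of four):

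| Threshold | A | B | C |
|---|---|---|---|
| $500 | 0.77 / 0.04 | 0.93 / 0.93 | 0.77 / 0.06 |
| $1,000 | 0.80 / 0.36 | 0.92 / 0.91 | 0.80 / 0.76 |
| $2,000 | 0.79 / 0.61 | 0.87 / 0.87 | 0.79 / 0.79 |
| $10,000 | 0.77 / 0.72 | 0.79 / 0.79 | 0.77 / 0.77 |

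Hand check of the pairwise value in A at $1,000: the mean NB difference is 1,000 × 10 + 5,000 = 15,000; its SD is √[2 × (8,000² + 10,000²)] = 18,111; z = 0.83, giving 0.80.

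**The case against.** Several points on the other side are sound.

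- **The pairwise curve answers its own question correctly.** A reader might infer that the plan overstates the probability for 1HP. The documents do not support that: the SAP names the pair openly and nowhere calls the result the probability that 1HP is best of four. The overstatement arises only if the curve is read that way.
- **The SAP goes part of the way.** It simulates every strategy, speaks of curves for each strategy, and ties only the primary one to 1HP v 3HP. A four-strategy curve may be intended. What is missing is a statement of the comparator set.
- **The planned results would often reveal the problem.** A reader might infer that the report would present 3HP as good value while 1HP is cheaper and better. But the primary contrast and its plane would show that dominance directly. In step 3 the planned set includes 1HP v none ($889). An alert reader who sees that this exceeds 1HP v 6H ($712) could deduce that 6H is extendedly dominated. This softens the point, but it leaves the dominance analysis to the reader.
- **Making the randomised contrast primary is defensible.** 6H and no treatment are modelled, not trial arms.
- **More may be written elsewhere.** Protocol 8.3, 15.2.2 and 15.8.4 refer to a separate economic protocol or plan, which is not among the documents. It would therefore be wrong to conclude that no four-way analysis is planned anywhere. However, SAP 10.3.2 already fixes the ratio, model, horizon, discount rate and primary curve, and the SAP's introduction gives limiting data-driven analysis as its goal. The comparison rule belongs with those choices.

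**Conclusion.** The point holds as a specification gap in a secondary outcome. As written, SAP 10.3.2 compares four strategies by pairwise DALY ratios, has no ordering or dominance step, omits 6H v no treatment, and leaves the comparator set of the wider CEACs undefined. A dominated strategy can therefore show an acceptable ratio against 6H or no treatment. The primary curve gives an upper bound on the probability that 1HP is the best of four.

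The size for this trial cannot be computed. Under the assumed inputs the gap runs from about zero, when 1HP is both cheapest and most effective as the plan expects, to 73 percentage points (0.77 v 0.04, scenario A at $500). Those figures show that the two probabilities can differ; they do not predict by how much here. The bound itself needs no assumed inputs. The two primary outcomes and the sample size are unaffected.

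**What to change.** Amend SAP 10.3.2 as follows:

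1. Order the four strategies by cost, remove dominated and then extendedly dominated ones, and report each remaining strategy's ICER against the next cheaper one on the frontier.
2. Keep the 1HP v 3HP plane and CEAC as the trial's head-to-head result, and also report incremental cost and incremental DALYs separately, because a negative ratio is ambiguous.
3. Add a four-strategy CEAC: at each threshold, the proportion of Monte Carlo draws in which each strategy has the highest net benefit.
4. Label any pairwise ICER that involves a dominated strategy.
5. Make the separate economic protocol consistent with these rules.

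The cost is SAP wording and slightly more analysis code on draws already planned; no new data are needed. The reported probability for 1HP may be less favourable than the pairwise one.

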6.1 Study Schema

Figure 1

6.2 Schedule of Procedures/Evaluations

See APPENDIX I

6.2.1 Laboratory Evaluations

Screening and follow-up

Hematology Hemoglobin, hematocrit, red blood cells, white blood cell count, and platelets.

Blood Chemistry Sodium, potassium, chloride, creatinine, and albumin.

Liver Function Tests Total bilirubin, AST (SGOT), ALT (SGPT), and alkaline phosphatase.

These tests should be performed at any time during the treatment and posttreatment phase if the participant exhibits signs suggestive of hepatitis (e.g., fatigue, weakness, malaise, anorexia, nausea, vomiting, abdominal pain, pale stools, dark urine, chills, or jaundice).

Pregnancy Test Serum or urine β-HCG

Dried Blood Spot collection and temporary storage / batch testing Dried blood spot collection for presence of rifapentine

Urine collection Urine collection and point of care testing for presence of isoniazid

Sampling for NAT2 metabolizer genotype Dried blood spot or urine as determined by local capacity

Additional evaluations at Screening only HBsAg HIV-1 antibody test

6.3 Study duration is in APPENDIX I

TST or IGRA

7. INTRODUCTION

7.1 Background Information

Tuberculosis (TB) is the leading infectious killer globally and a major cause of illness and suffering. The World Health Organization has prioritized TB preventive therapy (TPT) for people with latent TB infection (LTBI) as a key strategy for controlling the epidemic. Prevention of TB with isoniazid preventive therapy (IPT) is effective and reduces morbidity and mortality, and has been the mainstay of TB prevention for decades. But for an intervention with an excellent evidence of efficacy, global uptake has been abysmal. Completion rates for IPT when it is administered are poor (Gillespie 2008; Durovni 2010), with a large proportion of patients unable to complete treatment (McClintock 2017; Sterling 2011). While uptake is influenced by a variety of factors, a critical element has been the duration of IPT, with adherence falling sharply over time in clinical trials and practice. Shorter course regimens have a much higher completion rate and are more acceptable to patients, clinicians, and programs.

7.2 Rationale

With support from the NIH and the CDC, we have pioneered the development of short-course, rifamycin-based TB preventive therapy (TPT) over the past 15 years. We have evaluated the efficacy of 3 months of weekly rifapentine and isoniazid (3HP) in people with and without HIV infection and showed that it is non-inferior to longer courses of INH, with better adherence and less toxicity. (Schechter 2006; Martinson 2011; Sterling 2011)

This regimen is now recommended as a first-line treatment for latent TB infection by the CDC and the World Health Organization, offering the potential of substantially increased uptake of TPT as part of the END TB Strategy. (WHO 2018)

More recently, supported by NIAID, we have shown that one month of daily rifapentine and isoniazid (1HP) is non-inferior to nine months of INH in people with HIV infection. (Swindells 2019) The availability of two innovative, new short-course TPT regimens offers a transformative opportunity to global TB control and achieving the End TB targets. However, a major question still requiring evidence is the safety of the 1HP regimen in people without HIV infection.

While the efficacy of 1HP can be assumed from its success in HIV-positive people, safety cannot. In the 1990s, several studies supported by NIAID and the CDC showed that a 2-month TBT regimen of rifampin and pyrazinamide (2RZ) was safe and efficacious in HIV-infected individuals.(Halsey 1998; Gordin 2000) However, subsequent research funded by NIAID, and experience in clinical practice, demonstrated that 2RZ was not safe in HIV-uninfected people, with high rates of hepatotoxicity and a number of deaths.(Schechter 2006; CDC 2001) No explanation for the difference in safety in HIV-infected and –uninfected people has ever been found, but this experience underscores the importance of demonstrating safety and tolerability in all target populations of new regimens for TBT.

While the 3HP regimen has been proved safe and effective in HIV-positive and –negative people, 1HP has only been shown to be safe and efficacious in HIV-positive people. An efficacy study in HIV-negatives would be useful for purposes of replication of the single study demonstrating the non-inferiority of 1HP, but such a trial would be extremely costly and time -consuming. The ACTG BRIEF TB trial took 6 years at a cost of >\$30 million with its sample size of 3000. It is likely that a non-inferiority efficacy trial in HIV negatives would require a sample size of at least 4500.

In the history of TB preventive therapy, a regimen that is efficacious in one population has always been efficacious in others. For 3HP, efficacy was found to be quite similar in HIV+ people and HIV-negative, as well as in children. What can differ, however, is toxicity and tolerability. As shown with the 2-month rifampin and pyrazinamide (2RZ) regimen, safety in people with HIV does not ensure safety in HIV-negative people. Thus, a safety and adherence study is both necessary and preferred.

1HP is now recommended by the WHO as a first-line regimen for treating latent TB infection in individuals >12 years of age. (WHO, 2020) To date, this regimen has only been studied in people with HIV infection. Because no formal studies of HIV seronegative people have been conducted, this trial will provide important information on the safety of the regimen in this population.

Because the 1HP regimen was developed exclusively with NIAID funding and sponsorship, the opportunity for the NIH to have full responsibility and credit for introducing a highly novel, short-course preventive therapy regimen that could radically transform TB control is at hand. A trial showing that 1HP is safe, tolerable, and more likely to be completed than 3HP has the potential to fundamentally alter TB control interventions worldwide.

Rationale for self-administered therapy

Directly observed therapy (DOT) has been the standard of care for treatment of active TB in clinical trials and clinical practice for many years. Based on WHO guidance that intermittent treatment using rifamycins should be done under DOT, the original trials of 3HP provided all treatment under supervision of a health care team member. (Schechter, Martinson, Sterling) Subsequently, it became apparent that DOT for TPT was not economically or clinically feasible in most settings outside the US, and a trial comparing self-administered with DOT 3HP was conducted by the TB Trials Consortium. The i-Adhere Study compared treatment completion of 3HP in individuals receiving TPT either by DOT or by self-administration, with or without SMS

reminders. The study was a non-inferiority trial with an NI margin of 15% for treatment completion. Adherence in the self-administered arms was measured by electronic pill caps. In the primary analysis, self-administered 3HP failed to show non-inferiority to DOT, with rates of 87.2% completion for DOT vs. 75% (lower 95% CI 68.9%) for self-administered and 76.4% (lower 95% CI 71.3) for self-administered with SMS reminders. In the pre-planned analysis of participants enrolled in the US, however, non-inferiority of self-administration was demonstrated. On the basis of these results, the CDC now endorses self-administration of 3HP as a treatment option, and the WHO guidelines likewise support self-administration. The BRIEF-TB study used self-administered 1HP and showed a high treatment completion rate (97%) and excellent adherence. Based on global guidelines and the impracticality of using DOT for the millions of patients who require TPT, we will give both 1HP and 3HP by self-administration.

Rationale for including adolescents

Inclusion of children in clinical trials of tuberculosis treatment increasingly has been called for to support the rational use and increased availability of antituberculosis medications for children (Burman 2008, McKenna 2014). Tuberculosis disease characteristics, presentation, diagnosis, and treatment are similar for adults and adolescents. Rifapentine currently is approved as TPT in the United States for use in persons as young as 2 years old (Priftin® package insert 2018). Rifapentine pharmacokinetic results have been found to be similar between adults and adolescents down to age 12 (Marshall 1999). Rifapentine 900 mg once weekly, with isoniazid for 12 weeks has been used to treat children for LTBI (Villarino 2015): the rifapentine-containing regimen was found to be as safe and effective as a 9-month daily isoniazid regimen, among 552 children age 2-17 years old treated with the rifapentine-containing regimen. Daily dosing of rifapentine in children <12 has not been studied, however; the IMPAACT network is currently planning a trial of 1HP in children. Inclusion of adolescents is, therefore, appropriate, but inclusion of children <12 is not.

8. OBJECTIVES and HYPOTHESES

8.1 **Primary Objectives**

To compare treatment success (completion of treatment with \geq 90% adherence) of 1HP with 3HP in HIV-uninfected adults and adolescents at increased risk of TB.

To compare the safety of 1HP with 3HP in HIV-uninfected adults and adolescents at increased risk of TB.

